8.3. Efficacy Evaluations

A secondary objective of both the Phase 1a and 1b portions of the study is to assess the following efficacy endpoints:

- ORR
- DCR
- DOR
- PFS
- OS

ORR, DCR, DOR, and PFS will be assessed according to RECIST v1.1 (Eisenhauer et al. 2009).

PFS is defined as the time from the date of study enrollment until the date of the first observed radiographically documented PD or death due to any cause, whichever comes first. Overall survival, including 1- and 2-year survival rates, is determined from the date of first treatment until death due to any cause.

Patients may continue to be treated with the combination therapy until a confirmed progression is documented per irRECIST.

Following computerized axial tomography (CT) scan or magnetic resonance imaging (MRI) during the screening period, investigators will assess tumor response modified for confirmation of progression (irRECIST) every 6 weeks (\pm 5 working days) for up to 24 weeks. Confirmatory scans will be preferably obtained at the next routine scheduled imaging time point (that is, 6 weeks) and no earlier than 4 weeks later. After 24 weeks, tumor assessments will be conducted every 12 weeks. Additional radiologic assessments are permissible at the discretion of the investigator. The method of assessment used at baseline should be used consistently for a patient throughout the trial. Refer to [Attachment 1](#) for details regarding the timing of specific efficacy measures.

Immune-Related RECIST (irRECIST)

Immunotherapeutic agents such as pembrolizumab may produce antitumor effects by potentiating endogenous cancer-specific immune responses. The response patterns seen with such an approach may extend beyond the typical time course of responses seen with cytotoxic agents, and can manifest a clinical response after an initial increase in tumor burden or even the appearance of new lesions. Standard RECIST may not provide an accurate response assessment of immunotherapeutic agents such as pembrolizumab (Wolchok et al. 2009). Therefore, RECIST 1.1 will be adapted to account for the unique tumor response characteristics known to occur with pembrolizumab treatment (irRECIST) and additionally assessed using these criteria. Adaptations for irRECIST are detailed in [Attachment 8](#).

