10.8. Efficacy

The following endpoints will be listed and summarized: individual best overall response (BOR) using RECIST version 1.1 criteria, DOR, PFS, and OS. In addition, the following endpoints will be listed and summarized using irRECIST criteria: BOR, DOR, and PFS by irRECIST. Rates including ORR and DCR will be computed and the estimates will be reported with exact 95% CIs. Time-to-event variables including PFS, DOR, and OS will be analyzed using the Kaplan-Meier method (Kaplan and Meier 1958). Survival curves will be used to summarize the data. If data are sufficiently mature, medians will be reported with the 95% CIs. In addition, for each time-to-event variable, survival rates at adequate time points will be reported (for example, 3, 6, and 12 months).

Individual changes in the tumor size over time will be presented graphically using line plots. The change in tumor size corresponding to the best response based on target lesions for each patient will be represented in waterfall plots by cohort.

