6.11. Efficacy Analyses

6.11.1. Efficacy Definitions

The following definitions for efficacy endpoints will be used:

Overall response rate (ORR) is the proportion of patients who achieved a complete response (CR) or partial response (PR) out of all patients treated. Tumor responses will be measured and recorded using the appropriate guidelines [RECIST 1.1 (Eisenhauer et al. 2009)].

Best response is determined as the best response recorded from start of study treatment until PD or recurrence.

Disease Control Rate (DCR) is the proportion of patients who achieved a best response of complete response (CR), partial response (PR) or stable disease (SD) out of all patients treated.

Immune-related objective response rate (irORR) is defined as the proportion of treated patients achieving a best overall response of PR or CR per irRECIST, particularly, the best overall response by irRECIST closely related to confirmed response by RECIST. Immune-related ORR further captures responses after unconfirmed PD and does not require confirmation. For example:

- If the best response by RECIST v.1.1 is CR, then the best response by irRECIST is CR.
- If the best response by RECIST v.1.1 is PR, SD, or PD, the best response by irRECIST is the best response over the initial assessment (prior to PD by RECIST v.1.1) and the confirmation stage.

Overall, the best response by irRECIST should be the same or better than the best response by RECIST v.1.1 criteria. In addition, patients who do not have any postbaseline tumor response assessments for any reason are considered non-evaluable and will be included in the denominator when calculating the response rate.

Immune-related disease control rate (irDCR) is defined as the proportion of treated patients achieving a best overall response of CR, PR or SD per irRECIST.

[figure not shown]
Duration of Response will be calculated for ORR and is defined only for responders (ie. CRs and PRs). It is measured from the date of first evidence of a confirmed response to the date of first progression of disease or the date of death due to any cause, whichever is earlier. For each patient who is not known to have died or to have had a progression of disease as of the data-inclusion cut-off date, duration of response will be censored at the date of last objective response assessment prior to the date of any subsequent systemic anticancer therapy.

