Duration of Stable Disease will be calculated only for patients with best response of stable disease, CR or PR. It is measured from the date of start of treatment to the date of first progression of disease or the date of death due to any cause, whichever is earlier. For each patient who is not known to have died or to have had a progression of disease as of the data-inclusion cut-off date, duration of stable disease will be censored at the date of last objective response assessment prior to the date of any subsequent systemic anticancer therapy.

[figure not shown]
Duration of response by irRECIST is defined from the date of first documented irCR or irPR (responder) to the date of irPD or the date of death due to any cause, whichever is earlier.

Graphic Example:

Scenario 1: The initial PD is confirmed at the next scan (consecutive PD). The efficacy variables by irRECIST and RECIST are the same.

Scenario 2: The initial PD is not confirmed at the next scan (non-consecutive PD). The efficacy variables by irRECIST and RECIST v.1.1 are different.

In addition, the best response after initial PD may be listed. Other efficacy analysis based on irRECIST may be performed for exploratory analysis.

Change in tumor size will be assessed in each patient with measurable disease using radiographic imaging. Tumor size is the sum of the tumor measurements for target lesions at each tumor evaluation. Change in tumor size is defined as the percent change in tumor size from

the baseline evaluation to the minimum post-dose evaluation. Other definitions of CTS may be explored (including specific time points, and AUC formulations).

Progression-free survival (PFS) time is defined as the time from the date of start of study treatment to the first date of PD (symptomatic or objective) or death due to any cause, whichever occurs first. For patients who are not known to have died or progressed as of the data-inclusion cut-off date, PFS time will be censored at the date of the last objective progression-free disease assessment prior to the date of any subsequent systemic anticancer therapy.

Immune-related progression-free survival (irPFS) is defined as the date from the treatment started date to the time of PD assessed by irRECIST.

- If the initial PD is confirmed, then the date of immune-related (ir)PD is the initial PD date by RECIST v.1.1.
- If the initial PD is unconfirmed, then the date of irPD is the date of second PD.

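### The SAP's irPFS leaves out death and gives no progression date when a first PD is never rescanned, so read literally it runs above RECIST PFS on average

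*SAP*

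**What the plan says.** SAP 6.11.1 gives the endpoint in one sentence: "Immune-related progression-free survival (irPFS) is defined as the date from the treatment started date to the time of PD assessed by irRECIST". Two bullets then date irRECIST progression (irPD). If the initial PD is confirmed, its own date is used. Otherwise: "If the initial PD is unconfirmed, then the date of irPD is the date of second PD". No censoring rule specific to irPFS follows.

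The neighbouring definitions in the same section all include death:

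- RECIST PFS runs to the "first date of PD (symptomatic or objective) or death due to any cause, whichever occurs first", and it has its own censoring sentence: "PFS time will be censored at the date of the last objective progression-free disease assessment".
- Duration of response runs to the "date of first progression of disease or the date of death due to any cause, whichever is earlier", and duration of stable disease is handled the same way.
- Duration of response by irRECIST runs "to the date of irPD or the date of death due to any cause, whichever is earlier".

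Protocol 8.3 defines PFS by "radiographically documented PD or death due to any cause, whichever comes first". Protocol 10.8 lists "BOR, DOR, and PFS by irRECIST" among the planned summaries without defining it separately.

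On rescanning, Protocol 8.3 and Table ATT.8.3 (Attachment 8) exempt clinically unstable patients from repeat imaging. These patients stop treatment, and any rescan is at the investigator's discretion. Footnote c of Attachment 1 limits 6-weekly progression follow-up to patients who stopped treatment for a reason other than progression.

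**The concern.** There are two gaps. First, a patient who dies without irPD has an event for PFS but none for irPFS. A responder who dies that way even has an event for irRECIST duration of response and not for irPFS. Second, a patient whose first PD is never rescanned has no second PD, so the dating rule yields no irPD date. These are probably the patients doing worst, so censoring them is informative.

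PFS by irRECIST is a named secondary objective in both phases (Protocol 5.2.1.2 and 5.2.2.2), and SAP 6.11.2 reports irPFS by Kaplan-Meier alongside PFS. In a single-arm checkpoint-inhibitor combination study, an irPFS longer than PFS invites reading as late or atypical immune benefit. With these gaps, the difference would mix true pseudoprogression with lost events, and the curves would not show which is which.

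**Working it through.** The documents state no PFS or irPFS figure, so there is nothing to reproduce. The check has three parts.

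**1. One scan interval, exact Kaplan-Meier.** Take n at risk, D deaths before the scan, p first PDs at the scan, and u of those never rescanned. Assume no pseudoprogression. Deaths are censored at the previous scan and un-rescanned PDs at the PD scan.

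- PFS factor = (n − D − p)/n
- Literal irPFS factor = (n − D − p + u)/(n − D)

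With illustrative counts n = 25, D = 2, p = 10, u = 3, PFS = 13/25 = 0.52 and irPFS = 16/23 = 0.70.

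**2. Closed form.** Assume constant hazards and no pseudoprogression. Let d be the share of first events that are deaths without PD and q the share of first PDs never rescanned. The share of PFS events lost is L = 1 − (1 − d)(1 − q). Then irPFS(t) = PFS(t)^(1 − L), and the median is multiplied by 1/(1 − L).

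| L | True 6-month PFS of 20% becomes | Median multiplied by |
|---|---|---|
| 5% | 22% | 1.05 |
| 10% | 24% | 1.11 |
| 20% | 28% | 1.25 |
| 30% | 32% | 1.43 |

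Now assume a median time to PD of 3 months, so that irPFS(6) = 2^(−6/3) = 0.250 when q = 0.

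- Median time to death 14 months: d = 3/17 = 17.6%; PFS(6) = 2^(−6/3 − 6/14) = 0.186; true median 2.47 months.
- Median time to death 24 months: d = 3/27 = 11.1%; PFS(6) = 2^(−6/3 − 6/24) = 0.210; true median 2.67 months.
- d = 5%: PFS(6) = 0.250^(1/0.95) = 0.232; true median 3 × 0.95 = 2.85 months.

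Omitting death alone therefore adds 0.250 − 0.232 = 0.018 up to 0.250 − 0.186 = 0.064 at 6 months. It lengthens the median from those values to 3.00 months, a gain of 0.15 to 0.53 months. With q = 0.1 or 0.2, irPFS(6) = 0.250^(1 − q) = 0.287 or 0.330, and the median is 3/(1 − q) = 3.33 or 3.75 months.

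**3. Simulation on the protocol's scan grid** (6-weekly to week 24, then 12-weekly). These are the results of 4,000 trials of 31 patients per scenario, with median time to PD 3 months and 12 months of follow-up. Lost events were censored either at the event date or at the last progression-free scan.

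| Median time to death (months) | q | PFS events lost | Mean 6-month gap (points) |
|---|---|---|---|
| 57 | 0 | 6% | 2 |
| 24 | 0 | 13-14% | 4-5 |
| 24 | 0.1 | 22% | 8-9 |
| 14 | 0.2 | 37% | 14-17 |

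A second simulation used 25 patients, scan timing varied by ±7 days and 800 replicates per setting. With median PD 3 months, median death 12 months and no deliberate skipping of rescans, the 6-month rate was 0.196 for PFS and 0.281 for literal irPFS. The medians were 2.87 and 4.02 months. About 5% of patients in that setting still went un-rescanned because death or the end of follow-up came first. The mean shift was upward in every setting tried. Literal irPFS fell below PFS in at most 3.5% of replicates at any time point examined, because early censoring shrinks the risk set.

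With death counted and un-rescanned PD dated at the initial PD, irPFS matched PFS exactly when there was no pseudoprogression (0.196 for both). With 5-10% pseudoprogression it exceeded PFS by 1.5 to 4 points, which is the intended irRECIST effect.

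**The case against.** The strongest reply is that the documents, read together, already put death in irPFS. The protocol's PFS includes it, Protocol 10.8 asks for the same endpoint under irRECIST, and the SAP's own irRECIST duration of response counts it. A careful programmer would probably add it, and the death part of the bias would then vanish. That is plausible, and the gap does look like a drafting omission. But the sponsor wrote death into every neighbouring definition, so its absence here is ambiguous at best. This reading also does nothing for the never-rescanned PD.

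A second reply is that silence is not censoring: the only specific sentence in SAP 6.3 concerns patients who withdrew without progression. That is true. Still, SAP 6.3 offers no treatment for time-to-event data other than censoring, and a patient with no event in a Kaplan-Meier analysis is censored somewhere. SAP 6.1 lets derivations follow sponsor standards at the time of analysis, but that leaves the rule unwritten until open-label data are visible.

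Third, the un-rescanned share may be small. Repeat imaging is the default, and Attachment 1 marks tumour assessments at Visits 801 and 802 and in long-term follow-up, with the comment redacted. The SAP's graphic example is also not shown, although both of its captions presuppose a next scan. This stands as a limit on size.

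Fourth, the death scenarios are assumptions and may overstate deaths before PD. That is fair, and the 5% case is included for this reason. On the other side, the continuous-time median shift of 0.15 to 0.53 months understates what a scan grid can produce (2.87 against 4.02 months above).

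Last, the endpoint is descriptive, and individual PFS and OS are listed. That bears on priority and does not make the definition correct.

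**Conclusion.** The concern holds. As written, irPFS omits death, and its dating rule fails for a case the protocol allows. Following the text literally biases irPFS upward against RECIST PFS on average, though not in every dataset.

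The size cannot be fixed from the documents. Under constant hazards, no pseudoprogression, a median time to PD of 3 months and 5-18% of first events being deaths without PD, omitting death adds about 2-6 points at 6 months. That is inside the 15-20 points of uncertainty that Protocol 10.1.1 gives for N = 31, but it is systematic. It becomes large only if un-rescanned PDs are common: 14-17 points when 37% of events are lost. The median may move by a few tenths of a month in continuous time, or by more than a month on the scan grid.

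The gap should be fixed before analysis. It affects the interpretation of a secondary descriptive endpoint and nothing confirmatory.

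**What to change.** In SAP 6.11.1:

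1. Define irPFS as the time from first dose to irPD or death from any cause, whichever comes first.
2. If a first RECIST PD has no repeat scan, take the initial PD date as the irPD date. Use the second-PD date only when a repeat scan was done and did not confirm progression. Apply the same rule to irRECIST duration of response.
3. Censor patients with neither irPD nor death at the last assessment that is progression-free by irRECIST before any subsequent systemic anticancer therapy. A repeat scan that fails to confirm a first PD then counts as progression-free.
4. Treat symptomatic PD the same way in PFS and irPFS when they are compared. SAP PFS counts it, irPFS does not mention it, and Protocol 8.3 requires radiographic PD. This is a separate mismatch, best settled in the same edit.

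The cost is SAP wording and derivation code. No new scans or data are needed. Reported irPFS would be slightly less favourable, and any remaining excess over PFS could be attributed to unconfirmed progression.

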6.11.2. Efficacy Analyses

Reported lesion data (target/ non-target), investigator assessment of response, duration of response/stable disease, PFS and OS will be listed for all patients.

Efficacy data will be summarized according to treatment. If data warrant, efficacy analyses of ORR and irORR will also be presented separately for each sarcoma histology and treatment.

The following efficacy summaries will be provided:

- ORR, DCR, irORR and irDCR will be presented with exact 95% CI.
- Time to event endpoints including PFS, DOR, irPFS, irDOR and OS will be summarized descriptively using the Kaplan-Meier method. Survival curves will be used to summarize the data. If data are sufficiently mature, medians will be reported with the 95% CIs. In addition, for each time-to-event variable, survival rates at adequate time points will be reported (for example, 3, 6, and 12 months).
- Change in tumor size over time will be presented graphically using line plots. Minimum change in tumor size will be presented using a waterfall plot.

6.12. Bioanalytical and Pharmacokinetic/Pharmacodynamic Methods

Unless stated otherwise, the Lilly pharmacokineticist will be responsible for the PK and PK/PD analyses and will be detailed separately in a PK/PD analysis plan.

Serum olaratumab concentrations at different time points will be summarized by descriptive statistics. Additional analyses utilizing the population pharmacokinetic approach may also be conducted if deemed appropriate.

PK and PD data will be analyzed with appropriate standard nonlinear analytic software. Pharmacokinetic parameter estimates for olaratumab will be calculated by standard noncompartmental methods of analysis.

The primary parameters for analysis will be maximum concentration (C_{max}) and area under the concentration-time curve ($AUC_{[0-t_{last}]}$, $AUC_{[0-\infty]}$) of olaratumab. Other noncompartmental parameters, such as time of half-life ($t_{1/2}$), apparent clearance (CL/F), and apparent volume of distribution (V/F) may be reported. Additional exploratory analyses will be performed if warranted by data and other validated pharmacokinetic software programs (for example, NONMEM) may be used if appropriate and approved by Global Pharmacokinetic management. The version of any software used for the analysis will be documented and the program will meet the Lilly requirements of software validation.

6.13. Safety Analyses

All safety summaries and analyses will be based upon the safety analysis set. Safety data will be listed and summarized with patient counts and percentages in each treatment arm. Details of the analyses are described in the following sections.

6.13.1. Extent of Exposure

A summary of exposure will be provided for each study drug, including cycle received, cumulative dose and duration of therapy, for all treatment patients per treatment arm and total.

A summary of dose intensity will be provided for each study drug, for all treatment patients per treatment arm and total. Percent dose intensity is calculated as:

$100 \times (\text{actual cumulative dose taken (mg)} / \text{planned cumulative dose (mg)})$

Note that planned dose is the same as actual dose if there are no dose modification or cycle delays.

A summary of dose adjustments will be provided for each study drug, including dose omissions, dose reductions and cycle delays, and the corresponding reasons for dose adjustment, for all patients per treatment arm and total. If the reason for dose modification is due to an AE, the associated AE will be provided.

A Napoleon plot of treatment duration, treatment received and reason for discontinuation will be provided.

6.13.2. Adverse Events

A listing of all AEs by patient will be presented. This listing will include patient number, AE (reported term and preferred term [PT]), event start and end dates, CTCAE grade, relationship to study drug/procedure, seriousness, and outcome. A listing of serious AEs (SAEs) will be produced using the similar format.

An overall summary will be provided for AEs. The number and percent of evaluable patients will be summarized by treatment for each category below. The summary will provide counts for all AEs, and AEs related to study treatment.

- Patients with at least one treatment-emergent AE (TEAE)
- Patients with at least one grade 3 or 4 TEAE

- Patients with at least one SAE
- Patients who discontinued due to AE
- Patients who discontinued due to SAE
- Patients who died due to AE on study treatment
- Patients who died due to AE within 30 days of discontinuation from study treatment

Treatment-emergent adverse events (TEAE) are defined as follows:

- Any event that first occurred or worsened in severity after baseline, based on the CT LLT term and CTCAE severity grade. This means that any episode of the same AE with the same grade as at baseline that starts after the first dose of study treatment will not be defined as treatment-emergent, even if now considered drug related.
- Or any pre-existing condition [PEC] (emerged prior to signing the informed consent) or any AE (emerged after signing the informed consent) for which the outcome of the AE is ongoing at the time of first dose but has increased in severity (CTCAE grade) following the start of study treatment, regardless of causality.

As per Lilly's standard operating procedures, all "related", "probably related," "possibly related," or "does not know" AEs and SAEs will be defined as related to study drug.

MedDRA v16.1 (or higher) will be used when reporting AEs by MedDRA terms. TEAEs will be summarized by System Organ Class [SOC] and by decreasing frequency of PT within SOC.

TEAEs will be summarized by CTCAE grade, including the total for maximum Grade 3 and 4, and Grade 3, 4 and 5. These summaries will be provided for events regardless of study drug causality, and repeated for events deemed by the investigator to be related to study medication.

Dose-limiting toxicities (DLTs) and DLT-equivalent toxicities will be listed for all patients on therapy. Dose escalation phase 1a will be driven by safety using a 3+3 scheme.

Medical history and PECs will be listed for each patient.

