6.1. Study Population

6.1.1. Inclusion Criteria

Patients may be included in the study if they meet all of the following criteria during screening prior to the first dose of study drug.

- [1] Have histologically confirmed diagnosis of unresectable locally advanced or metastatic STS, not amenable to curative treatment and after available standard therapies (per local guidelines) have failed to provide clinical benefit, or been deemed inappropriate candidates for additional standard treatments by the investigator.

Patients with a diagnosis of Grade 1 liposarcoma (atypical lipomatous neoplasms) are eligible if there is histological or radiographic evidence of evolution to more aggressive disease.

- [2] Is ≥ 18 years of age.
- [3] Are willing and able to perform written informed consent for the trial and are amenable to compliance with protocol schedules and testing.
- [4] Have measurable or nonmeasurable but evaluable disease as defined by Response Evaluation Criteria in Solid Tumors (RECIST version 1.1 [v1.1]; Eisenhauer et al. 2009).

[5] Have adequate organ function, as defined in the table below, with all screening labs performed within 14 days of first dose of study treatment.

System	Laboratory Value
Hematological	
Absolute neutrophil count (ANC)	$\geq 1.5 \times 10^9/L$
Platelets	$\geq 100 \times 10^9/L$ (platelet transfusions are not allowed within 2 weeks prior to Study Day 1, see Exclusion Criterion [20])
Hemoglobin	$\geq 9 \text{ g/dL}$ or $\geq 5.6 \text{ mmol/L}$ (packed red blood cell transfusions are not allowed within 2 weeks prior to Study Day 1, see Exclusion Criterion [20])
Renal	
Creatinine or Measured or calculated ^a creatinine clearance (CrCl) (GFR may be used in place of creatinine or CrCl) (Attachment 7)	$\leq 1.5 \times \text{ULN}$ or $\geq 60 \text{ mL/min}$
Hepatic	
Total bilirubin	$\leq 1.5 \times \text{ULN}$
AST (SGOT) and ALT (SGPT)	$\leq 2.5 \times \text{ULN}$ or $\leq 5 \times \text{ULN}$ for patients with liver metastases
Coagulation	

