If female and of childbearing potential, has a negative serum or urine pregnancy test within 72 hours prior to the first dose of study medication, agrees to use a highly effective method of birth control during the study and for up to 120 days following the last dose of the study drugs, and is not breastfeeding. If the urine test is positive or cannot be confirmed as negative, a serum pregnancy test will be required.

A highly effective method of birth control is defined as one that results in a low failure rate (that is, $<1\%$ incidence of pregnancy per year) when used consistently and correctly, such as contraceptive implants, injectables, combined oral estrogen or progestogen-only contraceptives associated with inhibition of ovulation, some intrauterine contraceptive devices (IUDs), sexual abstinence, or a vasectomized partner. For patients using a hormonal contraceptive method, information regarding the study drugs under evaluation and their potential effect on the contraceptive should be addressed.

Abstinence as a method of birth control is acceptable if it is the established and preferred method of contraception for the patient.

- [10] Have an anticipated life expectancy of ≥ 3 months.
- [11] Inclusion Criterion [11] has been deleted.

6.1.2. ***Exclusion Criteria***

Potential study patients may not be included in the study if any of the following apply during screening.

- [12] Have disease that is suitable for local therapy administered with curative intent.
- [13] Have received any previous systemic therapy (including investigational agents) targeting PD-1/PDL-1 or PD-1/PDL-2 signaling pathways (including previous participation in Merck MK-3475 trials). Prior treatment with olaratumab is allowed. Prior therapy with other immune checkpoint inhibitors, including but not limited to, anti-CD137 antibody or anti-cytotoxic T-lymphocyte-associated antigen-4 (CTLA-4) antibody, is not permitted.
- [14] Have had chemotherapy, targeted small molecule therapy, or radiation therapy within 2 weeks and/or monoclonal antibody treatment within 4 weeks prior to study Day 1 or who have not recovered (that is, to \leq Grade 1 or baseline) from the effects of previously administered agents.
 - Neuropathy (\leq Grade 2) or nonserious and nonlife-threatening toxicities, such as alopecia, altered taste, or nail changes, are an exception to this criterion.

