10.4. Safety Analyses

All patients who receive at least 1 dose of any study therapy will be evaluated for safety and toxicity.

The Medical Dictionary for Regulatory Activities (MedDRA) Version 16.1 (or higher) will be used when reporting AEs by MedDRA terms. The MedDRA Lower Level Term (LLT) will be used in the treatment-emergent computation. Treatment-emergent adverse events will be summarized by System Organ Class (SOC) and by decreasing frequency of Preferred Terms (PT) within SOC.

Safety analyses will include summaries of the following:

- DLTs at each dose level
- AEs, including severity and possible relationship to study drug
- SAEs, including possible relationship to study drug
- AEs leading to dose adjustments
- discontinuations from study treatment due to AEs or death
- treatment-emergent abnormal changes in laboratory values
- treatment-emergent abnormal changes in vital signs

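### A drug-related recurrence of a baseline condition at its baseline grade is counted in no by-term table of drug-related adverse events

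*SAP*

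**What the plan says.** SAP 6.13.2 opens its definition of a TEAE with "Any event that first occurred or worsened in severity after baseline, based on the CT LLT term and CTCAE severity grade". It then spells out the consequence for an event whose term and grade are unchanged from baseline: a fresh episode which "starts after the first dose of study treatment will not be defined as treatment-emergent, even if now considered drug related". A second bullet admits conditions still present when dosing begins if their grade later rises, whatever the cause.

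The tables by system organ class (SOC) and preferred term (PT), and those by CTCAE grade, are TEAE tables. The grade summaries are given regardless of causality and then "repeated for events deemed by the investigator to be related to study medication". SAP 6.18 builds the registry's Other category from events that are both treatment-emergent and non-serious.

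Protocol 10.4 lists among the required safety summaries "AEs, including severity and possible relationship to study drug". It also fixes the matching level: "The MedDRA Lower Level Term (LLT) will be used in the treatment-emergent computation".

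**The concern.** The rule looks only at term and grade. An event can be present at baseline, clear, and return after dosing as a separate episode that the investigator attributes to study drug. If it returns at the old grade it is not a TEAE, and the SAP says expressly that attribution makes no difference.

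Safety and tolerability is the primary objective of both phases, and there is no control arm. Readers will take the table of related events by term as the count of what investigators attributed to the combination. As specified, that count can leave out related events, and nothing in the table shows how many. The omission can act in one direction only.

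**Working it through.** This is a question of definition, so the main check traces which events reach which outputs.

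**Step 1. Classification under SAP 6.13.2**
- Different term, same grade: TEAE.
- Same term, higher grade: TEAE.
- Baseline event that continues unbroken without worsening: not a TEAE, and there is no new onset.
- Same term, present at first dose, resolves, then restarts at the same grade: not a TEAE, even if judged related.
- Same term, resolved before first dose, then restarts at the same grade: unclear. The baseline rule in SAP 6.1 is written for change-from-baseline analyses. It does not say whether a resolved episode sets an AE's baseline grade.

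**Step 2. Where an excluded related episode appears**
- Not counted: the TEAE tables, their drug-related repeat (6.13.2), and the registry Other table (6.18).
- Reported with no stated TEAE condition: the listing of all AEs with dates, grade and relationship, and the DLT and DLT-equivalent listing (6.13.2); the dose-adjustment summary with its associated AE (6.13.1); serious AEs, all and related, and the special-interest and clinical-interest events (6.13.3); laboratory listings and grade summaries (6.13.4). The overall summary rows for serious AEs, discontinuations and deaths are also free of it.

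A non-serious related recurrence is therefore visible patient by patient. No specified table by term counts it as drug related.

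**Step 3. Can such baselines occur?** Entry permits them.
- Inclusion [8] holds clinically significant toxicity from prior therapy to Grade 1 or lower.
- Exclusion [14] exempts neuropathy up to Grade 2, and says that "nonserious and nonlife-threatening toxicities, such as alopecia, altered taste, or nail changes, are an exception to this criterion".
- Inclusion [5] allows AST and ALT up to 5 times the upper limit of normal "for patients with liver metastases".

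As an illustration, suppose an ALT elevation recorded at Grade 2 at baseline normalises, then returns at Grade 2 and is judged immune-related. (The documents do not reproduce the CTCAE thresholds, so the baseline grade is an assumption.) Table JGDQ.4 calls for pembrolizumab to be withheld. The event would reach the AE listing, the dose-adjustment summary and the laboratory outputs. It would not reach the related-TEAE tables. Nor would it be an event of clinical interest unless bilirubin was also raised and the alkaline phosphatase condition met.

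**Step 4. Size.** The documents give no count of such recurrences. The only AE-rate figures are in Table JGDQ.8, at N = 6 + 25 = 31 (protocol 10.1.1). Exact Clopper-Pearson intervals reproduce all six rows; for example, 10/31 = 0.32 (0.17 to 0.51).

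Now assume that 10 of 31 patients truly had a given related AE, and that k of them had only same-grade recurrences. The reported rate is (10 − k)/31:

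| k (assumed) | Reported | 95% CI |
|---|---|---|
| 0 | 32.3% | 16.7 to 51.4 |
| 1 | 29.0% | 14.2 to 48.0 |
| 2 | 25.8% | 11.9 to 44.6 |
| 3 | 22.6% | 9.6 to 41.1 |
| 5 | 16.1% | 5.5 to 33.7 |

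Each patient lost costs 1/31 = 3.2 points. A patient leaves a related row only if no other related TEAE falls under that preferred term. One related worsening above the baseline grade keeps the patient in.

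**The case against.** The strongest reply is that new or worse than baseline is a convention which the SAP discloses. Protocol 10.4 itself calls for a treatment-emergent computation and gives no rule on recurrence, so there is no direct contradiction. The convention keeps flares of background disease out of the tables, and anything excluded can be traced in the AE listing beside the listing of pre-existing conditions. All of that stands. It does not answer the point that a listing is not an incidence table, and that the drug-related repeat is the only by-term count of non-serious related events.

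A reader might infer more than the documents support:
- *That drug-related toxicity generally drops out, or that the primary safety objective rests on the filtered tables.* Only the same term at the same grade is affected. Dose escalation rests on DLTs and the wider safety review, and the outputs in Step 2 carry no TEAE condition.
- *That entry guarantees such baselines.* It allows them. The loss also needs resolution and a return at exactly the same grade, and nothing shows that neuropathy, alopecia, taste or nail changes behave that way.
- *That the label CT LLT lets two different events match because they share only a system organ class.* Protocol 8.1.2 requires a CTCAE term, actual or coded, and a grade for every AE. It also requires verbatim text, which is mapped to MedDRA. What remains is an undefined prefix.
- *That the bias can be quoted as an assumed baseline prevalence times an assumed recurrence rate.* Both inputs would be invented, and the product is an upper bound because it includes patients who also worsen.

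**Conclusion.** The point holds in a limited form. As written, the SAP gives an incomplete by-term count of drug-related AEs: non-serious related recurrences at the baseline grade are missing from the drug-related tables and from the registry Other table. Given the entry limits on prior toxicity, the loss should fall mainly on low-grade events, although other pre-existing conditions could carry a higher grade. The direction is certain. The size is unknown, and the table in Step 4 rests on assumed values of k.

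The documents do not require the TEAE definition to be rewritten. Making every related event treatment-emergent would be a debatable change to a stated convention. It would also bring in background flares of uncertain cause, since protocol 8.1.2 applies possibly related to links that are not probable. This is a cheap improvement to reporting, not an error that threatens the study's conclusions.

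**What to change.** Keep the TEAE definition and make three edits to SAP 6.13.2.

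1. Build the drug-related tables, or add one table by SOC, PT and maximum grade, from all AEs judged related that start on or after first dose, whatever the baseline grade. Retain related TEAEs that are worsenings of a condition already present at first dose, because their recorded start may precede dosing.
2. State how an AE's baseline grade is set when the earlier episode resolved before first dose.
3. Replace CT LLT with the MedDRA LLT named in protocol 10.4.

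The cost is a SAP amendment and one derivation or output. Start and end dates, grade and relationship are already in the planned AE listing, so no new data are needed. The registry Other table would not change, because it is defined by TEAE status.

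The downside is slightly higher related-AE rates. Some will be background recurrences, because the SAP counts possibly related and does-not-know attributions as related. Showing the new table beside the related-TEAE table lets a reader see how much the rule removes.
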